#### **Study Measures:**

The primary outcome is sustained viral response at 12 weeks post treatment (SVR12). Secondary outcomes include a) HCV treatment initiation, b) HCV Treatment completion (filled final prescription and self-reported > 90% HCV treatment pills taken), c) engagement with harm reduction resources, d) substance use, e) perceived stigma, and f) engagement in addiction treatment resources. Exploratory endpoints include a) treatment satisfaction with hepatitis C treatment, adapted from the single-item Medication Satisfaction Questionnaire, and b) reinfection vs. virologic relapse/failure.

Adherence to Phone Visits: Adherence to these phone visits is defined as +/- 5 days

Prescreen, baseline and follow-up surveys collected in the field or via phone will first be documented on paper forms. These will then be entered into REDCap by the RA. The source documents will be kept in a locked file cabinet in a secure location.

Qualitative interviews will be recorded on an encrypted recorder and stored on a secure, encrypted computer.

Survey data will be used to determine HCV status of participants with a detectable plasma HCV RNA, which were collected on or after SVR12 timepoint (either 12 weeks after end of treatment for those who initiated treatment or 32 weeks after randomization for those who did not initiate treatment). The primary SVR12 outcome will be sustained viral response 12 weeks after treatment for participants who initiated treatment within 6 months. Participants who did not start treatment within 6 months will be considered treatment failure. Measuring detectable plasma HCV RNA for both participants who initiated and did not initiate within 6 months of randomization will provide a framework to assess for potential biasing impact of spontaneous clearance on assumption of treatment failure for participants who did not initiate treatment within 6 months.

**Probable Relapse/Failure:** Probable virologic relapse or failure is defined as a detectable plasma HCV RNA 12 weeks or more after the end of treatment if a) participant denies any injection drug use, or b) participant injecting drugs but notes 100% adherence to recommendations on Safe injection practices, including use of clean works (cooker, cotton, rinse) with every injection.

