**Probable Reinfection:** Probable reinfection is defined as a detectable plasma HCV RNA 12 weeks or more after the end of treatment if a) participant completes full course of DAA regimen, and b) participant notes injection behavior of substantial risk, including i) Receptive use of injection equipment (needles, cotton, cooker) from someone of either unknown HCV serostatus or known positive serostatus on one or more occasion and ii) use happened between end of treatment and HCV RNA test

**Indeterminant Relapse vs Reinfection:** Indeterminant virologic relapse vs reinfection is defined as a participant with a detectable plasma HCV RNA 12 weeks or more after the end of treatment in participants a) not completing DAA regimen, and b) with injection behavior of substantial risk, as noted above.

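### The relapse and reinfection rules never use the participant's own SVR12 result and, separately, leave some injectors in no class (exploratory endpoint)

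*Combined protocol and SAP*

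**What the plan says.** Study Measures lists "b) reinfection vs. virologic relapse/failure" among the exploratory endpoints. It states the source of the classification: "Survey data will be used to determine HCV status of participants with a detectable plasma HCV RNA, which were collected on or after SVR12 timepoint".

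Three classes follow, each starting from detectable RNA at least 12 weeks after treatment ended.

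- **Relapse/failure:** that viraemia plus a condition on reported behaviour alone, "if a) participant denies any injection drug use, or b) participant injecting drugs but notes 100% adherence to recommendations on Safe injection practices". There is no condition on treatment completion and no time window for the behaviour.
- **Reinfection:** "Probable reinfection is defined as a detectable plasma HCV RNA 12 weeks or more after the end of treatment", provided that "participant completes full course of DAA regimen" and that the participant reports receptive use of equipment from a source of unknown or positive HCV status, at least once, between end of treatment and the RNA test.
- **Indeterminate:** the same viraemia in participants "not completing DAA regimen, and b) with injection behavior of substantial risk", with the risk behaviour defined as for reinfection.

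There is no residual class, and no rule mentions the participant's RNA at SVR12.

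On whether RNA is tested after SVR12, the document disagrees with itself. The compensation table under Recruitment Methods pays for laboratory tests for reinfection at 36 weeks after treatment, and the Study Measures wording reaches beyond the SVR12 timepoint. The Phase 2 table under Participant Assessments marks HCV RNA only at screening and at 12 weeks post-treatment. The text below it limits phlebotomy to those two visits, and the 36-week survey is conditional on the participant qualifying.

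**The concern.** A reinfection endpoint should separate people who never cleared the virus from people who cleared it and became viraemic again. The most direct evidence in the trial for that distinction is the SVR12 RNA, which is also the primary outcome. The rules leave it out. One participant can therefore be a responder in the primary analysis and a probable relapse or failure in the exploratory table, on the strength of a survey answer.

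The second worry is that the classes do not cover every viraemic injector. Cases that fit no rule would have to be placed by judgement after the data are seen, in a trial that is not blinded. At stake is the breakdown of viraemia into reinfection and failure, not the comparison of SVR12 between arms.

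**Working it through.** The documents give no rates, sample size or power for this endpoint, so the check is logical: write down the three rules and apply them to every combination of their inputs.

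**Inputs (Study Measures).** SVR12 RNA: undetectable or detectable (2). Treatment course: complete or incomplete (2). Reported injecting: the five levels in the table. Qualifying receptive use means use of equipment from a source of unknown or positive status. All combinations assume detectable RNA at or after 12 weeks post-treatment. Cells: 2 × 2 × 5 = 20.

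**Class assigned (identical for undetectable and detectable SVR12 RNA).**

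| Reported injecting | Course complete | Course incomplete |
|---|---|---|
| None | relapse/failure | relapse/failure |
| Injects, 100% safe practice | relapse/failure | relapse/failure |
| Below 100% safe, no qualifying receptive use | no class | no class |
| Qualifying receptive use only before end of treatment | no class | no class |
| Qualifying receptive use between end of treatment and RNA test | reinfection | indeterminate |

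**Counts over both SVR12 results.**
- Relapse/failure: 2 behaviours × 2 courses × 2 = 8
- Reinfection: 1 × 1 × 2 = 2
- Indeterminate: 1 × 1 × 2 = 2
- No class: 2 × 2 × 2 = 8
- Total: 8 + 2 + 2 + 8 = 20, with no cell in two classes

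**Defect 1.** The SVR12 result changes the label in 0 of the 10 behaviour-by-course pairs. With an undetectable SVR12 result and later viraemia, 4 of 10 cells are labelled relapse/failure.

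**Defect 2.** With detectable RNA at SVR12 itself, 4 of 10 cells have no class. This gap needs no later sample.

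**Sensitivity to the time window.** The fourth row assumes that the relapse rule, which has no window, looks at behaviour during treatment as well as after it. If it covers only the time after treatment, that row merges into the first three. That leaves 2 × 4 = 8 cells for each SVR12 result: 4 relapse/failure, 1 reinfection, 1 indeterminate, 2 with no class. The gap shrinks but stays.

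**After the fix below.** All undetectable-then-detectable cells go to one class. For detectable SVR12 RNA with a single window, the 8 cells become 4 relapse/failure, 1 reinfection, 1 + 2 = 3 indeterminate and 0 unclassified.

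**The case against.** The strongest reply is that little depends on this. The endpoint is exploratory, its classes are called probable, and no hypothesis or model under Data Analysis uses them. That stands. A reader might infer that the rules misstate the trial's efficacy result. They do not: someone undetectable at SVR12 remains a success in the primary analysis whatever label follows.

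Second, the first defect requires an RNA test after SVR12. If the assessment schedule is right, the RNA being classified is the SVR12 result itself and the contradiction cannot occur. This also stands as a condition, but two other places in the document foresee a later test.

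Third, the list of risk behaviours is introduced as an inclusion, so it may not be closed. On an open reading other unsafe injecting could qualify and the gap could be filled, but substantial risk would then have no stated boundary. The gap is therefore claimed on the listed criteria only.

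Three further inferences go too far.

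- The unclassified injectors do not cause the relapse labels; the two defects are independent.
- Non-starters are not a third defect of the same weight. No class fits them because they have no end of treatment, but Study Measures counts participants who do not start within 6 months as treatment failures and explains that their RNA is measured to examine spontaneous clearance.
- It would be wrong to declare all viraemia after SVR12 to be proven reinfection. Phase 2 admits opioid users who do not inject, so a denial may be true, and the documents give no rate of late relapse or of under-reported injecting.

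**Conclusion.** The point holds as two separate defects in the rules for an exploratory endpoint.

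1. No class uses the SVR12 RNA, so a recorded responder who is later viraemic can be labelled relapse or failure (4 of the 10 cells with undetectable SVR12 RNA). This is conditional on RNA being tested after SVR12, and the passages on that must be reconciled.
2. On the listed criteria the classes are not exhaustive, even at the SVR12 draw: 8 of 20 cells have no class with the time window included, or 2 of 8 for each SVR12 result if every rule looks only at the post-treatment period.

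These are counts of logical combinations. They do not say how many participants would be affected, which depends on reported behaviour that the documents do not give. The primary SVR12 analysis is untouched, so the priority is low.

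**What to change.** Amend the definitions in Study Measures, using the same inputs in both arms.

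1. Among treated participants, split first by observed SVR12 RNA. Report undetectable-then-detectable cases as their own class, viraemia after SVR12 (presumed reinfection), and not as relapse/failure. Show reported injecting descriptively within it.
2. Apply the existing behaviour rules only to participants with detectable RNA at SVR12, with one risk window (end of treatment to RNA test) in all three.
3. Assign every unmatched case to indeterminate. This includes later viraemia with no SVR12 sample: a result counted as non-suppressed only because it is missing is not a detectable RNA.
4. Report viraemic non-starters separately as untreated.
5. Reconcile the compensation table, the assessment schedule and the phlebotomy statement on whether RNA is tested at 36 weeks. If it is not, step 1 has no cases to classify and steps 2 to 4 still apply.

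The cost is revised wording and a few lines of code; the rule itself needs no new data, although the class in step 1 can be filled only if a later RNA is taken. The downside is that a late relapse after SVR12 would fall in the presumed-reinfection class, which is why that class should be named as a presumption and shown on its own.

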#### Qualitative Interview Procedures:

We will conduct qualitative interviews by telephone with a sample of purposively selected study participants. An interview guide will be used, and interviews will last approximately 45 minutes. Up to 35 interviews will be conducted by trained researchers. Participants will be reimbursed \$50 for their participation. The participant qualitative interview guide will assess tele-HCV acceptability, satisfaction, perceived quality of care, advantages and disadvantages relative to face-to-face appointments, and barriers and facilitators to treatment initiation and adherence. Questions will also examine the role of peers in facilitating telemedicine, medication access, and adherence.

We will also conduct virtual focus groups with peer support specialists and tele-HCV clinicians. The peer support specialist focus group guide will assess tele-HCV and HCV treatment barriers and facilitators; peer specialist activities and adaptations; and advantages and disadvantages of tele-HCV. The clinician focus group guide will assess peer-assisted tele-HCV procedures; barriers and facilitators; experiences engaging with specialty pharmacies, payers, and peers; and clinical considerations related to tele-HCV.

## **Data and Specimens**

### **a) Handling of Data and Specimens**

**Survey Data:** Participants complete brief surveys regarding symptoms and substance use at baseline, 4, end of treatment, 12 weeks post-end of treatment, and 36 weeks post end of treatment. Survey data will be collected from PWUD by Research staff or PCCs, via 2-in-1 laptops or local office PCs or hand-held devices using REDCap data collection, detailed below (Privacy, Confidentiality, and Data Security).

**Biologic Specimen Data:** Biological specimen data will be stored at Peace Health, Mercy Medical, and Molecular Testing Labs. Serum samples drawn for DBS validation will be completed at Peace Health and Mercy Medical and shipped to Molecular Testing Labs.

**Participant Locator Form Data:** We will collect identifying information (name, social security number, date of birth, address, phone numbers, employer information, e-mail address, and other contact information) to use for follow-up of patient for future studies. The locator form also asks what forms of social media are commonly used and where the individual commonly spends most of their time. Participants will be contacted on social media using a highly-private account specific to the study. Index after the study is completed. Data will be collected on paper and the original will be stored in a locked file cabinet at HIV Alliance for the duration of the study. Data will be abstracted into a spreadsheet in Box, maintained behind the OHSU firewall, for future use. Only HIV Alliance and OHSU will have access to this information.

### **b) Sharing of Results with Subjects**

Results of HCV tests will be shared with the participant.

### **c) Data and Specimen Banking**

De-identified specimens may be shared with other researchers, including the National Rural Opioids Initiative data coordinating center at University of Washington, Molecular Testing Labs, and other National Rural Opioids Initiative collaborators. This study does not include genetic research. Participant contact information (including name, date of birth, address, and Social Security Number) will be entered by study staff into a spreadsheet in OHSU BOX and stored behind the OHSU firewall. Participants who indicate willingness to be contacted for future studies in the consent form may be contacted and offered participation in future studies. [name] will serve as the guardian of this repository. [name] will ensure that data is received and released according to OHSU policy and the IRB approved repository protocol. A repository sharing agreement will be executed each time data is released for research purposes. [name] will track all releases of data. Should a participant withdraw their consent, [name] will indicate this in an additional spreadsheet that will be kept in OHSU BOX, and will ensure that the participant's data is destroyed. Participants from OR-HOPE indicate in the informed consent form whether or not they agree to future contact regarding participation in additional studies.

To certify documentation of local IRB approval to the OHSU IRB, a copy of the approval letter from the contributing site will be included in the submission to the repository. Consent to contact for future studies and to store data will be obtained from the participant when the participant signs the optional section of the informed consent form. To document whether the person from whom the data was obtained signed a legally effective consent and authorization, study staff will review the signatures and date from the original consent form and indicate the date that it was signed in the data collection spreadsheet.

To ensure security and confidentiality during the collection of data, only study staff will be entering data into the data collection spreadsheet in OHSU BOX. Only OHSU's PI and Research Assistant and HIV Alliance study staff will have access to the data in OHSU BOX. Only [name] will be able to grant access to the BOX files. A Certificate of Confidentiality will be obtained to further protect the sensitive information obtained from participants.

## Data Analysis:

Pre-specified analyses for this study will be intention-to-treat (ITT) comparisons between telemedicine and treatment as usual (local treatment referral) on primary and secondary outcomes. Prior to conducting these analyses, we will compare baseline covariate distributions (demographics, etc.) between randomized groups using standardized mean differences (SMDs) and bivariate statistical tests (e.g. t-tests, Chi-square tests). If a significant imbalance in any variable is noted, i.e., a SMD > 0.25 and  $p < .2$ , we will include that variable as a covariate in future analyses. All primary and secondary analyses will utilize generalized linear (mixed) models (GLMMs) with distributions and link functions appropriate for the distribution of the outcome variable. Fixed effects of interest in the models will be timepoint (baseline, 4 weeks, end of treatment, 12 weeks post-treatment, 36 weeks post-treatment), randomized group (telemedicine vs. TAU), and their interaction. If more than one timepoint is included in the analysis, GLMMs will include person-level random intercepts to account for repeated measurements on subjects. Hypotheses will be tested using between-group comparisons at each timepoint of interest, or within-group comparisons across timepoints.

Hypothesis 1: Participants randomized to receive tele-HCV treatment will have superior SVR-12 rates compared to those randomized to TAU (referral for local treatment).

Analytic strategy: We assess the effect of telemedicine versus TAU on SVR at 12 weeks post-treatment completion using logistic regression. Missing HCV viral load data will be considered non-suppressed in the main ITT analysis. Sensitivity analyses will include a per-protocol analysis and a repeat of the main analysis using multiple imputation of missing data.

Hypothesis 2: Participants randomized to receive tele-HCV treatment will have superior rates of HCV treatment initiation (filled first prescription) compared to those randomized to TAU.

Analytic strategy: We assess the effect of telemedicine versus TAU on treatment initiation by 4 weeks post-baseline using logistic regression. Missing treatment initiation data will be considered non-initiated in the main ITT analysis. Sensitivity analyses will include a per-protocol analysis and a repeat of the main analysis using multiple imputation of missing data.

Hypothesis 3: Participants randomized to receive tele-HCV treatment will have superior rates of HCV treatment completion (filled final prescription and self-reported > 90% HCV treatment pills taken) compared to those randomized to TAU.

Analytic strategy: We assess the effect of telemedicine versus TAU on treatment completion by 12 weeks post-baseline using logistic regression. Missing treatment completion data will be considered incomplete in the main ITT analysis. Sensitivity analyses will include a per-protocol analysis and a repeat of the main analysis using multiple imputation of missing data.

Hypothesis 4: Participants randomized to receive tele-HCV treatment will have a higher likelihood of engagement with harm reduction resources, lower rates of substance use, lower stigma, and higher engagement in addiction treatment resources compared to those randomized to TAU (referral for local treatment).

Analytic strategy: We assess the effect of telemedicine versus TAU on these outcomes at all post-baseline timepoints using mixed effects regression models. Missing outcome data will be handled using full information maximum likelihood. We will conduct per-protocol analyses as sensitivity analyses.

**Qualitative Evaluation.** Audio-recorded interviews will be professionally transcribed; transcripts will be uploaded into qualitative analysis software (NVivo™). Comagine research staff create a coding scheme, conduct coding, and revise in an iterative process that has been successfully implemented by the study team in other mixed-methods projects. The qualitative data provides complementary information to illuminate and expand quantitative findings, including survey results and measures of treatment initiation and completion.

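### For H1 to H3 a baseline covariate enters the model only on chance imbalance; a short fixed list would be a cheap, minor improvement

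*Combined protocol and SAP*

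**What the plan says.** All of this is in the Data Analysis section of the combined protocol and SAP. Before the main comparisons, "we will compare baseline covariate distributions (demographics, etc.) between randomized groups using standardized mean differences (SMDs) and bivariate statistical tests". The trigger is: "If a significant imbalance in any variable is noted, i.e., a SMD > 0.25" and, in addition, p < .2. The consequence is that "we will include that variable as a covariate in future analyses".

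The models for the first three hypotheses name no covariate:

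- H1: "We assess the effect of telemedicine versus TAU on SVR at 12 weeks post-treatment completion using logistic regression".
- H2: "We assess the effect of telemedicine versus TAU on treatment initiation by 4 weeks post-baseline using logistic regression".
- H3: "We assess the effect of telemedicine versus TAU on treatment completion by 12 weeks post-baseline using logistic regression".

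The only fixed effects listed in general are timepoint, arm and their interaction. The Allocation section describes a central random assignment and gives no stratification factor, so no design variable is carried into the model either. For H1 to H3 the imbalance trigger is the only way a covariate can enter.

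**The concern.** Covariate adjustment in a randomized trial is useful when the covariate predicts the outcome. The trigger selects on something else. Under randomization, a difference between arms at baseline is chance and carries no information about prognosis. A variable that predicts SVR12 will usually be left out because it happens to be balanced, and one that does not may be let in because it happens not to be.

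Two things are at stake, both modest. The first is some precision in the primary comparison. The second is that the list of screened variables is open-ended, so the final H1 to H3 model cannot be written down now. In logistic regression, adding a prognostic covariate moves the odds ratio from a marginal to a conditional one, so which of the two is reported depends on the draw.

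**Working it through.** **Inputs.** From the documents: the thresholds SMD 0.25 and p < .2 (Data Analysis), and up to 200 Phase 2 participants (Number of Subjects). Assumed: 1:1 allocation, the absolute SMD, control rates, the treatment effect and covariate strengths. The documents give no Phase 2 power, alpha or event rates, so there is no stated figure to reproduce.

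**How often a given variable enters.** With n per arm, SE(SMD) ≈ √(2/n), for a continuous or two-level variable.

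- n = 100: √(2/100) = 0.141; 0.25/0.141 = 1.77; two-sided p = 0.077 (0.079 by t with 198 df). The p = .2 limit corresponds to SMD 1.282 × 0.141 = 0.181, so the SMD limit governs. Entry is about 8%; the variable is left out about 92% of the time.
- n = 75: √(2/75) = 0.163; 0.25/0.163 = 1.53; entry about 13%.
- n = 50: √(2/50) = 0.2; 0.25/0.2 = 1.25; p = 0.211. Now p < .2 governs and entry is 20%.

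Because p < .2 is always required, entry can never exceed 20%, so a given variable is left out at least 80% of the time at any size. Reading the SMD as signed would halve entry at n = 100 to about 3.9%.

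**How often the model changes at all.** If k independent variables are screened at n = 100, P(at least one enters) = 1 − (1 − 0.077)^k: 33% for k = 5, 55% for k = 10, 80% for k = 20. The plan does not give k.

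**Power.** Logistic simulation: n = 200, control rate 30%, treatment log-odds ratio 0.87, two-sided 5% Wald test, 20,000 runs. With no covariate effect this is about 30% v 51%: 0.429 × e^0.87 = 1.023 and 1.023/2.023 = 0.506. One continuous covariate:

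| Log-odds per SD | Unadjusted | Plan's rule | Always adjusted | Gain over rule (points) |
|---|---|---|---|---|
| 0 | 84.8% | 84.7% | 84.5% | −0.2 |
| 0.35 | 83.2% | 83.3% | 83.7% | 0.4 |
| 0.5 | 81.1% | 81.5% | 82.8% | 1.3 |
| 0.7 | 77.6% | 78.1% | 81.1% | 3.0 |
| 1.0 | 69.8% | 70.5% | 76.9% | 6.4 |

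A two-level covariate at 50% prevalence gives 83.2% v 83.6% (rule v always adjusted) for an odds ratio of 2, and 79.8% v 81.7% for 3. Other control rates (10,000 runs) give similar gaps. At 15% they are 66.7% v 68.1% (0.5 per SD) and 57.4% v 62.8% (1.0); at 50% they are 81.3% v 82.7% and 71.8% v 77.8%.

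**Type I error under the rule.** 0.050, 0.052 and 0.043 at 0, 0.5 and 1.0 per SD (Monte Carlo SE 0.0015). There is no inflation.

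**Effect measure.** Mean log-odds ratio when the rule does not trigger (unadjusted) v when it does (adjusted): 0.836 v 0.887 at 0.5 per SD, a gap of 0.051, or about one-sixth of a standard error of 0.30. At 1.0 per SD it is 0.735 v 0.881, a gap of 0.146.

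**Price of a fixed list.** One continuous covariate plus a three-level factor (3 df, assumed shares 50/30/20%), unadjusted v adjusted, 10,000 runs: 85.3% v 84.8% if nothing is prognostic; 81.4% v 82.5% if both are modest (0.35 per SD and per level step).

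**The case against.** The strongest reply is that this is a preference rather than an error. The rule is numeric, set in advance and uses baseline data only; the unadjusted comparison is valid under randomization. All of that stands. So does the point that the gain is near nil for weak covariates, and that the marginal-to-conditional gap is small against the standard error for a modest predictor.

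Four stronger readings are tempting, and the documents do not support them.

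- A reader might infer that the rule biases the trial or inflates false positives. It does neither. An SMD of 0.20 to 0.25, just under the cut-off, occurs 8.0% of the time and shifts the unadjusted log-odds ratio by about 0.10 at 0.5 per SD, but this averages to zero over randomizations.
- A reader might infer that a known predictor of SVR12 is being omitted. The documents name none; the 92% applies to any variable, prognostic or not.
- A reader might expect a large power gain. With three independent predictors at 0.5 to 0.8 log-odds per SD, simulated gains over the rule run from about 3 to 11 points, but nothing in the documents shows that such a set exists.
- A reader might extend the point to H4. The general model lists baseline among its timepoints ("Fixed effects of interest in the models will be timepoint (baseline, 4 weeks, end of treatment"), and H4 says "We assess the effect of telemedicine versus TAU on these outcomes at all post-baseline timepoints using mixed effects regression models". The two can be read together: baseline is a level in the model and the comparisons of interest come later. No contradiction is established.

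What survives is that selecting on imbalance is the wrong criterion, and that a better one needs no new data.

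**Conclusion.** The point holds as a minor, inexpensive improvement to H1 to H3. A given baseline variable is left out about 92% of the time at 100 per arm and at least 80% at any size, irrespective of its prognostic value, and the final model and the type of odds ratio are not known in advance. Validity is not in question. The power cost is about 0 to 1 point for one modest predictor and about 6 points only for a strong one (log-odds 1.0 per SD). These figures rest on assumed 1:1 allocation, the full 200 participants, and assumed event rates, treatment effect and covariate strengths. The actual gain in this trial is unknown.

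**What to change.** For H1 to H3, delete the imbalance trigger and the baseline significance tests as a way of choosing covariates. Before any outcome is examined by arm:

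- Fix a short list of baseline variables that are already collected and expected to predict the outcome. Age (linear) is one example; recruiting organization is another if it is recorded. The Setting section names HIV Alliance, BAFS and OWHN as recruiting, but the Phase 2 assessment table has no item for it.
- Allow sparse levels to be pooled using counts blinded to arm and outcome. This matters: at assumed shares of 85/12/3% the adjustment showed no gain, and the smallest level's coefficient failed to converge in about 10 to 12% of simulated runs.
- Adjust H1 to H3 for the list whatever the observed balance, and state that the odds ratio is conditional on it.
- Report SMDs descriptively and keep the unadjusted model as a sensitivity analysis.

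The cost is one paragraph and a few degrees of freedom (three for the example list in up to 200 people). The downside is about half a point of power if the chosen covariates turn out not to be prognostic. No change to H4 is requested.

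### Hypothesis 4 does not prespecify use of each outcome's baseline value in the between-arm contrast, which gives away precision at no benefit

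*Combined protocol and SAP*

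**What the plan says.** The general model text in Data Analysis covers all primary and secondary analyses. It reads "Fixed effects of interest in the models will be timepoint (baseline, 4 weeks, end of treatment, 12 weeks post-treatment" and continues to 36 weeks post-treatment, together with "randomized group (telemedicine vs. TAU), and their interaction". Where several timepoints are analysed, "GLMMs will include person-level random intercepts to account for repeated measurements on subjects". On testing: "Hypotheses will be tested using between-group comparisons at each timepoint of interest, or within-group comparisons across timepoints".

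The text specific to Hypothesis 4 reads "We assess the effect of telemedicine versus TAU on these outcomes at all post-baseline timepoints using mixed effects regression models", and then "Missing outcome data will be handled using full information maximum likelihood".

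The only route to covariate adjustment is the imbalance rule in the same section. Baseline distributions are compared between arms, and where a variable shows an SMD above 0.25 with p below .2, "we will include that variable as a covariate in future analyses". The comparison is described as one of baseline covariates, with demographics as the only named example. Baseline values of the outcomes are not mentioned.

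Those baseline values will exist. The Participant Assessments table schedules harm reduction and substance use treatment engagement, substance use and perceived stigma at baseline. Screening Procedures and the Phase 2 part of Intervention Design both place the baseline survey before randomization.

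**The concern.** Because the baseline survey precedes randomization, the arms have equal baseline means in expectation, and the baseline value of an outcome is usually among the best predictors of its later values. A between-arm contrast that uses this has a smaller variance. The plan does not say that it will be used. If baseline is a response level with arm, time and their interaction, each arm has its own free mean at every visit, baseline included. If baseline is left out of the response, it is not in the model at all. In neither case does the contrast at a follow-up visit condition on where the arms started.

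At stake are confidence intervals wider than the data allow, and results at every follow-up visit that lean in the direction of whatever chance difference existed at baseline. The two descriptions of the model also leave the analyst to choose between them.

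**Working it through.** **Inputs.** Phase 2 recruits up to 200 participants (Number of Subjects). The Allocation section gives no ratio, so 1:1 is assumed, n = 100 per arm. The documents give no SD, baseline-to-follow-up correlation (rho), effect size, power or dropout for Hypothesis 4, so there is no stated figure to reproduce. Assumed: a continuous outcome in SD units, rho of 0.3, 0.5 or 0.7, and two-sided alpha of 0.05.

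**Step 1: the contrast as planned.** With baseline in the response there are 2 arms x 5 visits = 10 means and 10 free fixed-effect parameters. Without it there are 2 x 4 = 8 of each. Either way the means are saturated. With complete data and an identity link, the contrast at a visit is then the raw difference in means at that visit, whatever the random intercept does. Its variance is 2/n, so SE = sqrt(2/100) = 0.141.

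**Step 2: with baseline used.** With the baseline value as a covariate, or a common baseline mean for both arms, the variance is 2(1 - rho^2)/n. The detectable difference at 80% power is (1.960 + 0.842) x SE.

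| | Planned | rho 0.3 | rho 0.5 | rho 0.7 |
|---|---|---|---|---|
| Variance factor, 1 - rho^2 | 1 | 0.91 | 0.75 | 0.51 |
| SE (SD units) | 0.141 | 0.135 | 0.122 | 0.101 |
| Variance saved | n/a | 9% | 25% | 49% |
| Detectable difference (SD) | 0.396 | 0.378 | 0.343 | 0.283 |
| Power for an assumed 0.4 SD effect | 80.7% | 84.3% | 90.4% | 97.7% |

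**Step 3: what the imbalance rule catches.** At 100 per arm an SMD of 0.25 corresponds to z = 0.25 x sqrt(100/2) = 1.77, p = 0.077. The p condition is therefore met whenever the SMD condition is, and the rule fires in about 7.7% of trials for a given variable. In the other 92% or so, an imbalance of up to 0.25 SD is left unadjusted.

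**Step 4: carry-over below the trigger.** With no treatment effect, the expected follow-up difference given a baseline difference d is rho x d. At d = 0.25 this is 0.075, 0.125 or 0.175 SD for rho 0.3, 0.5 or 0.7. At a typical chance imbalance of one SE (0.14 SD) it is about 0.04, 0.07 or 0.10 SD.

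**Step 5: simulation check.** Random-intercept models were fitted to 250 simulated trials with no treatment effect (100 per arm, 5 visits, rho 0.5, baseline in the response), reading the contrast at 12 weeks post-treatment.

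| | Free baseline means | Common baseline mean |
|---|---|---|
| SD of contrast, complete data | 0.142 | 0.121 |
| Slope on baseline difference, complete data | 0.51 | 0.02 |
| SD of contrast, about 30% dropping out | 0.151 | 0.135 |
| Slope on baseline difference, about 30% dropping out | 0.51 | 0.00 |

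With complete data the free-baseline contrast equalled the raw mean difference to within 3e-15. With dropout the likelihood does draw on baseline for the missing visits (0.151, against 0.161 for the raw difference), but the slope on the baseline difference stays at 0.51.

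**The case against.** **Validity.** A reader might infer that the planned contrast is biased. It is not. Over randomizations it is unbiased, its type I error is kept, and the 0.141 SE already includes chance baseline variation. Baseline as a response level is a standard analysis. This objection stands in full and limits the point to efficiency and to the result conditional on the imbalance that happens to occur.

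**Large imbalances.** A reader might also infer a sizeable spurious effect. In simulated null trials selected for a baseline difference above 0.25 SD (rho 0.5), the free-baseline model averaged 0.16 SD at follow-up. But that is the region where the plan's own rule may fire. With the baseline covariate added to that model the average was -0.02 SD, and with a common baseline mean it was 0.01. The -0.02 is a slight over-correction, negligible beside an SE of 0.12 to 0.14. So 0.16 cannot be offered as what the plan would produce. What survives is the imbalance below the trigger, and the uncertainty over whether the rule covers outcomes.

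**Which model.** It is tempting to say that the plan fits a free baseline mean in each arm. The general text supports this, but the Hypothesis 4 text refers to post-baseline timepoints and can be read as leaving baseline out of the response. In that case the rule, if it fired, would give ordinary baseline adjustment. Neither reading makes the adjustment unconditional, so the core point does not depend on the choice.

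**Transfer of the figures.** Hypothesis 4 words engagement as a likelihood and substance use as rates, so several outcomes may be binary or counts. The exact equality in Step 1 and the SEs above do not carry over to logit or log links. Eligibility also requires recent injection or opioid use, which may narrow baseline variation in substance use, and follow-up reaches week 56 for those who never start treatment, over which one constant rho may not hold. These are fair reasons to look towards the lower end of the range.

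**Conclusion.** The point holds as a free improvement, not as a fault of validity. The plan does not prespecify use of the baseline outcome in the Hypothesis 4 contrasts, and its only route to adjustment depends on the data and is unclear in scope. For a continuous outcome with complete data and 100 per arm, the cost is 9% of the variance at rho 0.3, 25% at 0.5 and 49% at 0.7. Imbalance that escapes the rule can shift a follow-up contrast by at most about 0.075, 0.125 or 0.175 SD at those correlations. The allocation ratio, rho and the continuous scale are assumptions. For binary or count outcomes a gain is expected in the same direction, but its size is not established here. Hypotheses 1 to 3 are single-timepoint logistic models and are not affected.

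**What to change.** State one model for Hypothesis 4 and reconcile the general text with it:

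- The response is the set of post-baseline visits. Fixed effects are visit, arm and arm-by-visit, and the baseline value of the same outcome is a prespecified covariate in every Hypothesis 4 model.
- For continuous outcomes, a constrained longitudinal model is an acceptable alternative: baseline stays in the response, both arms share one baseline mean, and arm enters only through post-baseline visits. For logit or count models the two forms are not the same model, so one must be chosen and named.
- Name the between-arm contrast to be reported at each visit.
- State that the imbalance rule does not apply to baseline values of the outcomes, since these are always adjusted for.

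The cost is a few sentences in Data Analysis. The baseline survey is already scheduled before randomization, so no new data or visits are needed. The change should be made before Hypothesis 4 outcomes are compared by arm.
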